APPENDIX 2: Time to Normalization of Respiratory Function

Patients who are on low flow O₂ (2-6L/min) should receive a daily trial off O₂ in the morning between 4-6 am – ~~10 am~~ 12 pm as described below.

Patient should be resting or sitting.

Patient should be fitted with pulse oximeter, and their SpO₂ should be checked once while on O₂ and then again ~~a minute~~ 3 – 5 minutes after turning off O₂ supplementation.

APPENDIX 3:

[REDACTED]

APPENDIX 4: [REDACTED]

[REDACTED]

[REDACTED]

[REDACTED]

[REDACTED]

[REDACTED]

APPENDIX 5: [REDACTED]

[REDACTED]

[REDACTED]

[REDACTED]

[REDACTED]

[REDACTED]

APPENDIX 5	98
APPENDIX 6	99
APPENDIX 7	SOFA Score Calculation	100
APPENDIX 8	DAIDS Toxicity Grading Tables for Clinical Abnormalities	101
APPENDIX 9	DAIDS Toxicity Grading Tables for Laboratory Abnormalities ..	103

PROTOCOL ACCEPTANCE FORM

TITLE: A PHASE 2 RANDOMIZED, DOUBLE-BLIND
PLACEBO-CONTROLLED TRIAL OF MHAA4549A,
A MONOCLONAL ANTIBODY, IN COMBINATION
WITH OSELTAMIVIR VERSUS OSELTAMIVIR FOR
TREATMENT OF SEVERE INFLUENZA A
INFECTION

PROTOCOL NUMBER: GV29216

VERSION NUMBER: 2

EUDRACT NUMBER: 2014-000461-43

IND NUMBER: 117,318

TEST PRODUCT: MHAA4549A

MEDICAL MONITOR: [REDACTED], M.D.

SPONSOR: Genentech, Inc.

I agree to conduct the study in accordance with the current protocol.

Principal Investigator's Name (print)

Principal Investigator's Signature

Date

Please return a copy of the signed form as instructed by the CRO. Please retain the original for your study files.

PROTOCOL SYNOPSIS

TITLE: A PHASE 2 RANDOMIZED, DOUBLE-BLIND
PLACEBO-CONTROLLED TRIAL OF MHAA4549A, A
MONOCLONAL ANTIBODY IN COMBINATION WITH
OSELTAMIVIR VERSUS OSELTAMIVIR FOR
TREATMENT OF SEVERE INFLUENZA A INFECTION

PROTOCOL NUMBER: GV29216

VERSION NUMBER: 2

EUDRACT NUMBER: 2014-000461-43

IND NUMBER: 117,318

TEST PRODUCT: MHAA4549A

INDICATION: INFLUENZA A

SPONSOR: Genentech, Inc.

Objectives

Safety Objectives

The safety objectives for this study are as follows:

- To evaluate the safety of MHAA4549A in combination with oseltamivir compared with placebo and oseltamivir in patients with severe influenza A, focusing on the nature, frequency, and severity of serious and non-serious adverse events, as well as effects on laboratory values, vital signs, electrocardiogram (ECG) parameters, anti-therapeutic antibodies (ATA), or other safety biomarkers

Efficacy Objectives

The primary efficacy objective for this study is as follows:

- To determine the time to normalization of respiratory function of patients dosed with MHAA4549A in combination with oseltamivir compared to patients dosed with placebo and oseltamivir

The secondary efficacy objectives for this study are as follows:

- To measure clinical failure after 24 hours post-infusion of study drug
- To determine the time to clinical resolution of vital signs
- To measure mortality in patients
- To determine changes in the extent and duration of viral shedding in upper respiratory samples
- To measure the duration of hospital and/or intensive care unit (ICU) stay
- To measure antibiotic usage for respiratory indications
- To measure the frequency and severity of the following secondary complications of influenza:
 - Pneumonia (hospital acquired pneumonia [HAP]/ ventilator acquired pneumonia [VAP])
 - Exacerbations of chronic lung disease
 - Myocarditis
 - Acute respiratory distress syndrome (ARDS)

- Otitis media
- Other related complications
- Readmission rates at 30 *and* 60 days after study treatment
- To measure duration of positive pressure ventilation (PPV)
- To measure readmission rates

Pharmacokinetic Objectives

The major pharmacokinetic (PK) objective for this study is as follows:

- To characterize the PK profile of MHAA4549A in serum

The exploratory PK objectives for this study are as follows:

- [REDACTED]
- [REDACTED]

Exploratory Objectives

The exploratory objectives for this study are as follows:

- [REDACTED]
- [REDACTED]
- [REDACTED]
- [REDACTED]
- [REDACTED]
- [REDACTED]
- [REDACTED]
- [REDACTED]

Study Design

Description of Study

This is a Phase 2b randomized, double-blind, placebo-controlled study designed to assess the safety and clinical activity of a single IV dose of MHAA4549A in hospitalized patients with severe influenza A in combination with oseltamivir versus a comparator arm of oseltamivir with placebo.

Patients will be randomized 1:1 into two treatment groups: a single intravenous (IV) dose of 3600 mg of MHAA4549A with oseltamivir or a single IV dose of placebo with oseltamivir. All patients will receive oseltamivir, a NAI, as standard therapy for a minimum of 5 days, starting after study drug administration. Oseltamivir at doses of 75 mg twice daily (BID) or 150 mg BID is permitted in order to be consistent with local standard of care practice. Treatment for longer than 5 days is permitted based on local investigator discretion. The patients must start Sponsor-supplied oseltamivir within 8 hours of study drug administration.

Patients hospitalized with an oxygen (O₂) or PPV requirement will be evaluated for influenza A infection. Enrollment in this study requires ongoing treatment within 24 hours of hospital admission with one of the following: any PPV or any supplemental O₂ to maintain oxygen saturation (SpO₂) > 92%.

A Sponsor-supplied rapid influenza test and/or a local polymerase chain reaction (PCR) test must be used as an aid in the diagnosis of influenza A infection.

At the time of randomization, patients who are eligible for enrollment will be randomized to receive either a single IV infusion of MHAA4549A or a single IV infusion of placebo that will be administered on Day 1. All patients must have the study drug infused within 48 hours of hospital admission or sooner if possible; therefore, screening must be completed within this

window. All patients will receive oseltamivir for a minimum of 5 days (10 doses), starting on Day 1 beginning no later than 8 hours after study drug administration. All patients will be followed for 60 days from the time of study drug administration.

Number of Patients

The study has a planned enrollment of approximately 334 patients (adult men and women) globally. Patients will receive MHAA4549A or placebo in 1:1 ratio. The number of patients on PPV should not exceed 45% of the total enrolled patients.

Target Population

Inclusion Criteria

Patients must meet the following criteria for study entry:

- Men or women ≥ 18 years of age on day of signing informed consent or obtaining surrogate consent from an authorized representative
- Diagnosis of influenza A as determined by *one or both of the following*:
 - A Sponsor-supplied rapid influenza test
 - A local molecular test (PCR)
- One of the following markers of severity within 24 hours of hospital admission:
 - Requirement for PPV, OR
 - Requirement for O₂ supplementation to maintain SpO₂ > 92%
- A negative urine or serum pregnancy test for women of childbearing potential
- Patients of reproductive potential must agree to use reliable means of contraception as described below as a minimum (adherence to more stringent local requirements may be required):
 - For female patients: Use of two acceptable methods of contraception throughout the trial, including the active treatment phase AND for 24 weeks after the last dose of MHAA4549A. Acceptable methods of contraception include: intrauterine device, systemic hormonal contraception (oral or depot), vaginal ring, tubal ligation of the female partner, vasectomy of the male partner, use of latex condoms plus spermicide by the male partner, or cervical cap plus spermicide (where the spermicide could be foam, vaginal suppository, gel, cream, etc.).
 - For male patients: Use of condoms for 30 days after dosing when circulating drug levels remain high.
 - Non-reproductive potential is defined below (but could be superseded by local definitions, if they are more stringent):
 - Women who are postmenopausal (i.e., spontaneous amenorrhea for the past year confirmed by an follicle stimulating hormone [FSH] level greater than 40 mIU/mL unless the patient is receiving a hormonal therapy for their menopause)
 - Women who are surgically sterile (i.e., hysterectomy, complete bilateral oophorectomy)
 - Men who are surgically sterile (castration)

Exclusion Criteria

Patients who meet any of the following criteria will be excluded from study entry:

- Pregnant or lactating, or intending to become pregnant during the study
 - Women who are not postmenopausal (≥ 12 months of non-therapy-induced amenorrhea) or who are not surgically sterile must have a negative urine or serum pregnancy test result within 2 days prior to study treatment
- Hypersensitivity to monoclonal antibodies or any constituents of study drug
- Investigational therapy within the 30 days prior to study treatment

- Received prior therapy with any anti-influenza monoclonal antibody therapy including MHAA4549A 8 months prior to study treatment
- Current treatment (within 7 days of dosing) with amantadine or rimantidine
- Patients who have taken more than a total of 3 days (6 doses) of approved anti-influenza therapy (i.e., oral oseltamivir, inhaled zanamivir, or oral ribavirin) in the period from onset of symptoms and prior to enrollment
- Admission > 48 hours prior to study treatment
- Onset of influenza symptoms > 5 days prior to study treatment
- Positive influenza B or influenza A + B infection within 2 weeks prior to study treatment
- High probability of mortality in the next 48 hours as determined by the investigator
- Patient requiring home or baseline oxygenation therapy
- Patient with history of chronic lung disease resulting in baseline SpO₂ < 95%
- Patient on chronic dose of corticosteroids exceeding 10 mg/day of prednisone or equivalent steroid dose for a duration of greater than 14 days within 30 days of entry into study
- Patients with the following significant immune suppression:
 - Bone marrow or solid organ transplant in the previous 12 months
 - Cancer chemotherapy in the previous 12 month
 - HIV infection with most recent CD4 < 200 cells/mL
 - Other significant immune suppression as determined by the investigator in discussion with the Sponsor Medical Monitor or representative
- Patient on extracorporeal membrane oxygenation (ECMO) at time of randomization
- Any disease or condition that would, in the opinion of the site investigator or Sponsor, place the subject at an unacceptable risk of injury or render the subject unable to meet the requirements of the protocol

Length of Study

This study will consist of the following study periods:

- A screening period of 48 hours, beginning at time of hospital submission
- A treatment period of 1 day, during which patients will receive a single dose of MHAA4549A or placebo and a *minimum* of 5 days of oseltamivir.
- A follow-up period beginning at hospital discharge through 60 days post study drug (MHAA4594A/placebo) administration

End of Study

The end of the study is defined as the first day when all patients have had a study completion visit or early termination visit or have otherwise been discontinued from the study.

Outcome Measures

Safety Outcome Measures

The safety outcome measures for this study are as follows:

- Adverse events and clinical laboratory abnormalities
- Vital signs, physical findings, ATAs, and clinical laboratory results during and following administration of MHAA4549A

Efficacy Outcome Measures

The primary outcome measure for this study is as follows:

- Time to normalization of respiratory function defined as:
 - The time to cessation of O₂ support resulting in a stable SpO₂ > 95% for at least 24 hours

The secondary efficacy outcome measures for this study are as follows:

- Clinical failure *after* 24 hours post-infusion of study drug defined as:

- Progression to increased O₂ requirement defined by an increase in oxygen supplementation from low flow oxygen (2–6 L/min) to high flow oxygen (>6 L/min) or from oxygen supplementation alone to any PPV
- Progression to ICU
- Prolonged ventilation or O₂ support defined by >2 weeks, or
- Death
- Time to clinical normalization of vital signs (3/5 criteria must be met):
 - SpO₂ > 95% without supplemental O₂ for at least 24 hours
 - Respiratory rate < 24 *breaths per minute* without supplemental O₂ for at least 24 hours
 - Core temperature < 37.2°C immediately prior to receipt of any antipyretic drug, and at least 6-8 hours from the last dose of antipyretic or core temperature > 36°C in patients who are initially hypothermic
 - Heart rate (HR) < 100/minute
 - Systolic blood pressure (SBP) > 90 mmHg
- All-cause mortality at Day 14, Day 30, and Day 60
- Influenza A viral load in nasopharyngeal samples
 - Area under viral load–time curve (AUEC)
 - Peak viral load
 - Time to resolution of infection
- Duration of hospitalization
- Duration of ICU stay
- Antibiotic usage for respiratory infections
- Complications of influenza:
 - Pneumonia (HAP/VAP)
 - Exacerbations of chronic lung disease
 - Myocarditis
 - Acute respiratory distress syndrome (ARDS)
 - Otitis media
 - Other related complications
- All-cause readmission at Day 30 and Day 60
- Duration of ventilation

Pharmacokinetic Outcome Measures

The primary PK outcome measures for this study are as follows:

- PK parameters for MHAA4549A in serum including total exposure (i.e., AUC), maximum observed concentration (C_{max}), clearance, half-life, and volume of distribution, when appropriate, as data allow

The exploratory PK outcome measures for this study are as follows:

- [REDACTED]
- [REDACTED]

Exploratory Outcome Measures

The exploratory outcome measures for this study are as follows:

- [REDACTED]
- [REDACTED]
- [REDACTED]

[REDACTED]

Investigational Medicinal Products

An investigational medicinal product (IMP) is a pharmaceutical form of an active substance or placebo being tested or used as a reference in a clinical trial, excluding marketed products unless the product is 1) used or assembled (formulated or packaged) differently than the authorized form, 2) used for an unauthorized indication, or 3) used to gain further information about the authorized form (Directive 2001/20/EC Article 2[d]). A non-investigational medicinal product (NIMP) is a medicinal product that is intended for use in a clinical trial per the protocol but does not fall under the definition of IMP. Further details can be found in the following EU guidance: Guidance on Investigational Medicinal Products and Non-Investigational Medicinal Products (effective March 2011).

MHAA4549A and Placebo

A single 3600-mg dose of MHAA4549A or dose of placebo will be delivered by IV infusion following dilution in 0.9% normal saline over approximately 60 minutes. Study drug should be delivered using a 0.22 µm in-line filter. Placebo will be identical to active MHAA4549A in formulation and appearance, but will not contain active drug substance.

Oseltamivir (Tamiflu®)

Sponsor-supplied oseltamivir (Tamiflu) 75 mg or 150 mg will be administered BID for a *minimum of 5 days*. Dosage and administration should follow local prescribing information for oseltamivir. Capsules can be opened and the granules administered via nasogastric tube, if required.

Statistical Methods

Primary Analysis

All efficacy analyses will be conducted according to the intent-to-treat principle and will include all patients who meet the following condition with patients allocated to the treatment arm to which they were randomized:

- Randomized patients who have confirmed influenza A infection by a central PCR test from Day 1 samples.

The primary and secondary efficacy analyses will include all randomized patients who are confirmed to be influenza A infected, with patients grouped according to the treatment assigned at randomization.

Time to event data will be computed using Kaplan-Meier methodology and stratified Cox proportional hazards models and will be summarized using n, median when estimable, hazard ratios, and 95% confidence intervals. Patients who are lost to follow-up (while event free) will be censored at the time that they are last known to be event free.

Estimation of the treatment difference of proportions and its 95% confidence interval will be calculated using stratum-adjusted Mantel-Haenszel methodology. For continuous endpoints, Analysis of Covariance methods (after appropriate transformation of data) will be used to estimate treatment differences at 95% confidence intervals.

Interim Analyses

Given the hypothesis-generating nature of this study, the Sponsor may choose to conduct up to two interim efficacy analyses. The decision to conduct an optional interim analysis and the timing of the analysis will be documented in the Sponsor's trial master file prior to the conduct of the interim analysis. The interim analysis will be performed and interpreted by members of the Sponsor study team and appropriate senior management personnel who will be unblinded at the treatment group level. Access to treatment assignment information will follow the Sponsor's standard procedures.

If conducted, an interim analysis would be for administrative purposes only (i.e., internal planning or decision making) and would not impact the conduct of the current study in any way. A nominal type I error penalty of 0.0001 will be taken. *In addition, as discussed below, the Sponsor will conduct interim safety analyses separate from and in conjunction with the above.*

Determination of Sample Size

A total of 334 patients will be enrolled in this study in order to obtain approximately 300 evaluable patients (an estimated dropout rate of 10%). It is assumed that the median time to normalization of respiratory function in the control arm is 5 days

LIST OF ABBREVIATIONS AND DEFINITIONS OF TERMS

Abbreviation	Definition
█	█
AE	Adverse event
AESI	Adverse events of special interest
ALT	Alanine aminotransferase
ARDS	Acute respiratory distress syndrome
AST	Aspartate aminotransferase
ATA	Anti-therapeutic antibody
AUC	Area under serum concentration–time curve
AUEC	Area under viral load–time curve
BID	Twice a day
°C	Celsius
C _{max}	Maximum observed concentration
C _{min}	Minimum observed concentration
CPK	Creatine phosphokinase
CRO	Contract (or Clinical) Research Organization
CTCAE	Common Terminology Criteria for Adverse Events
DAIDS	Division of Acquired Immunodeficiency Syndrome
ECG	Electrocardiogram
eCRF	Electronic Case Report Form
ECMO	Extracorporeal membrane oxygenation
EDC	Electronic data capture
FDA	Food and Drug Administration
FiO₂	Fraction of inspired oxygen
GCP	Good Clinical Practice
GGT	Gamma-glutamyl transferase
HA	Hemagglutinin
HAI	Hemagglutinin inhibition
HAP	Hospital Acquired Pneumonia
HIPAA	Health Insurance Portability and Accountability Act
HIV	Human Immunodeficiency Virus
HR	Heart rate
█	█
ICH	International Conference on Harmonisation
ICU	Intensive Care Unit
IEC	Independent Ethics Committee

Abbreviation	Definition
IMC	Internal Monitoring Committee
IMP	Investigational medicinal product
IND	Investigational New Drug (application)
IRB	Institutional Review Board
IRR	Infusion-related reactions
IV	Intravenous
LFTs	Liver function tests
mAB	Monoclonal antibody
NAI	Neuraminidase inhibitor
NP	Nasopharyngeal
PaO_2	Partial pressure of arterial oxygen
PCR	Polymerase Chain Reaction
PD	Pharmacodynamic
PK	Pharmacokinetic
PPV	Positive pressure ventilation
qPCR	Quantitative Polymerase Chain Reaction
QT_{cB}	QT interval corrected using Bazett's formula
QT_{cF}	QT interval corrected using Fridericia's formula
RBC	Red blood cell
RNA	Ribonucleic acid
SAE	Serious adverse event
SAP	Statistical analysis plan
SAP	Statistical analysis plan
SBP	Systolic blood pressure
SOC	Scientific Oversight Committee
SpO_2	Oxygen saturation by pulse oximetry
SUSAR	Suspected unexpected serious adverse reactions
ULN	Upper limit of normal
VAP	Ventilation Acquired Pneumonia

1. **BACKGROUND**

1.1 **BACKGROUND ON INFLUENZA**

Influenza A is a membrane-enveloped RNA virus that causes significant morbidity and mortality. Currently, there is a great need in hospitalized influenza patients for a parenteral therapeutic option that is well tolerated, can rapidly resolve influenza-related signs and symptoms, decrease mortality, reduce hospital and intensive care unit (ICU) stays, as well as have a prolonged window for initiation of treatment beyond the current standard of care (i.e., within 48 hours of the onset of flu symptoms).

Approximately 200,000 to 278,000 patients are hospitalized with severe influenza infections annually in the United States (U.S.) (Thompson et al. 2004; Zhou et al. 2012), and assuming the same rate reported in the U.S., an estimated 319,000 to 445,000 patients are hospitalized in the European Union (E.U.). Hospitalization due to severe influenza is associated with high mortality (4%–8%), ICU admission (5%–17%; Lee and Ison 2012), mechanical ventilation support in an ICU setting (7%–11%; Doshi et al. 2011), and prolonged hospital stays (5–9 days; Lee and Ison 2012). During a pandemic season, the outcomes may be more serious, with up to 34% of patients requiring ICU care and a mortality rate as high as 15% (Lee and Ison 2012).

Influenza infection is an upper and lower respiratory disease with a broad spectrum of presentations that can result in fever, shortness-of-breath, pneumonia, respiratory failure, secondary respiratory infections, and even death. The *standard of care* therapy for patients hospitalized with influenza consists of supportive measures and administration of available antiviral agents, primarily neuraminidase inhibitors (NAI) that include but are not limited to oseltamivir, zanamivir, and peramivir. However, a significant unmet medical need still exists in the severely ill patient population, as evidenced by the considerable degree of morbidity and mortality in this setting. To address this need, Genentech Inc. /F.Hoffmann-La Roche Ltd. (Genentech) is developing a highly-specific anti-influenza A (MHAA4549A) antibody therapy for treatment of hospitalized patients with severe influenza.

1.2 **BACKGROUND ON MHAA4549A**

1.2.1 **Nonclinical Background**

MHAA4549A is a human monoclonal IgG1 antibody (mAb) that binds to the influenza A virus and is cloned from a single-human plasmablast cell isolated from an influenza vaccinated donor (Nakamura et al. 2013). This antibody binds to a highly conserved epitope on the influenza A hemagglutinin stalk region, which allows broad neutralization of the influenza A virus by blocking the hemagglutinin-mediated, membrane-fusion event in the late endosome.

In vitro, MHAA4549A is capable of neutralizing all current clinically relevant influenza A strains. In vivo, efficacy of MHAA4549A has been demonstrated in mouse models of influenza A infection, both as a single agent and in combination with oseltamivir.

MHAA4549A specifically targets an epitope on the human influenza A hemagglutinin glycoprotein, which does not appear to be endogenously expressed on human or rat tissues and, therefore, is unlikely to be present in the absence of viral infection. Weekly administration of MHAA4549A (total of 5 doses) in Sprague-Dawley rats was well tolerated up to the maximum feasible dose of 150 mg/kg. *Ex vivo* tissue cross-reactivity study data showed no specific binding of MHAA4549A to any of the human or rat tissues examined.

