All patients will be followed and evaluated at minimum on a daily basis for the duration of their hospital stay consistent with the planned schedule of assessments. Any suspicion of bacterial superinfection should be thoroughly evaluated including microbiological confirmation, if possible. A follow-up study visit should occur on Day 14 ± 1 (if discharged before Day 14); Day 30 ± 4 days (if discharged before Day 30); and Day 60 ± 4 days (if discharged before Day 60).

Safety evaluations will be provided by an IMC and SOC, as defined in the IMC and SOC agreement (see [Section 3.1.2](#))

A schedule of assessments is provided in [Appendix 1a](#) and [Appendix 1b](#). A diagram of the study design is presented in [Figure 1](#).

Figure 1 Phase 2b Study Design (GV29216)

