4.9.3 Study Completion/Early Discontinuation Visit

Patients who complete all study visits through Day 60 are considered to have completed study. All patients who discontinue from *the* study early will be asked to complete *all assessments for the current visit day and for the early discontinuation visit without duplication*. Please see Schedule of Assessments provided in [Appendix 1a](#) for assessments performed at the Study Completion/Early Discontinuation visit.

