5.3.1 Adverse Event Reporting Period

Investigators will seek information on adverse events at each patient contact. All adverse events, whether reported by the patient or noted by study personnel, will be recorded in the patient’s medical record and on the Adverse Event eCRF.

After informed consent has been obtained **but prior to initiation of study drug**, only serious adverse events caused by a protocol-mandated intervention (e.g., invasive procedures such as biopsies, discontinuation of medications) should be reported (see [Section 5.4.2](#) for instructions for reporting serious adverse events).

After initiation of study drug, all adverse events, regardless of relationship to study drug, will be reported until the Day 60 visit or Early Discontinuation visit. After this period, the investigator is not required to actively monitor patients for adverse events; however, the Sponsor should be notified if the investigator becomes aware of any death or other serious adverse event that occurs after discharge, regardless of causality. The Sponsor should also be notified if the investigator becomes aware of a congenital anomaly/birth defect in a subsequently conceived offspring of a female patient exposed to study drug (see [Section 5.6](#)).

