5.5 POSTSTUDY ADVERSE EVENTS

At the time of study completion or study discontinuation, the investigator should instruct each patient to report to the investigator any subsequent adverse events that the patient or their personal physician believes could be related to prior study drug treatment or study procedures.

The investigator is not required to actively monitor patients for adverse events after the end of the adverse event reporting period (defined as 60 days after the dose of study drug). However, the Sponsor should be notified if the investigator becomes aware of any death, other serious adverse event, or non-serious adverse event of special interest occurring after the end of the adverse event reporting period, regardless of causality. The Sponsor should also be notified if the investigator becomes aware of the development of cancer or a congenital anomaly/birth defect in a subsequently conceived offspring of a female patient or a female partner of a male patient exposed to study drug.

The investigator should report these events by completing and faxing a paper Serious Adverse Event Reporting Form and fax cover sheet to Safety Risk Management using the fax numbers provided to investigators (see [Section 5.4.2.1](#)).

5.6 EXPEDITED REPORTING TO HEALTH AUTHORITIES, INVESTIGATORS, INSTITUTIONAL REVIEW BOARDS, AND ETHICS COMMITTEES

The Sponsor will promptly evaluate all serious adverse events including suspected unexpected serious adverse reactions (SUSARs) and non-serious adverse events of special interest against cumulative product experience to identify and expeditiously communicate possible new safety findings to investigators, IRBs, IECs, and applicable health authorities based on applicable legislation.

To determine reporting requirements for single adverse event cases, the Sponsor will assess the expectedness of these events using the following reference documents:

- MHAA4549A Investigator's Brochure
- Local prescribing information for oseltamivir

The Sponsor will compare the severity of each event and the cumulative event frequency reported for the study with the severity and frequency reported in the applicable reference document.

Reporting requirements will also be based on the investigator's assessment of causality and seriousness, with allowance for upgrading by the Sponsor as needed.

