APPENDIX 1b Schedule of Assessments: Follow-Up Period

- If a patient is discharged prior to Day 14, he/she will need to complete the following assessments for Day 14, Day 30, and Day 60 below.
- If a patient is discharged prior to Day 30 and after Day 14, he/she will need to complete the following assessments for Day 30 and Day 60 below.
- If a patient is discharged prior to Day 60 but after Day 30, he/she will need to complete the following assessments for Day 60 below.
- If patient is hospitalized for Day 14, Day 30, and/or Day 60, please refer to Appendix 1a.

Day (D)	D14 ± 1 (If discharged BEFORE D14)	D30 ± 4 (If discharged BEFORE D30)	Day 60 ± 4 (Study Completion) or Early Discontinuation
Concomitant medications ^a	x	x	x
Vital signs ^b	x	x	x
Electrocardiogram (12-lead) ^c	x	x	x
Weight & height, BMI ^d	x	x	x
Adverse events	x	x	x
Hematology ^e	x	x	x
Chemistry panel ^e	x	x	x
Coagulation panel ^e	x	x	x
Urinalysis ^e	x	x	x
Flu antibodies (HAI)	x	x	x
████████████████████		x	x
Serum for MHAA4549A PK measurements ^f	x	x	x
████████████████████	x	x	x
████████████████████	x	x	x
██████████		x	x
██████████		x	x
██████████		x	x
██████████		x	x

██████████; ATA = Anti-therapeutic antibodies; BMI = body mass index; D = day; Dx = diagnostics; eCFR = electronic Case Report Form; ECG = electrocardiogram; HAI = hemagglutinin inhibition; ██████████; PD = pharmacodynamics; PK = pharmacokinetic.

^a Concomitant medications should be recorded for 30 days prior to screening, through the study completion/early discontinuation visit. See exclusion criteria in [Section 4.5.2](#) for prohibited therapies.

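### The completion visit may fall on Days 56–59, so readmission by Day 60 can go unobserved in some discharged patients, and the sections disagree on when adverse-event reporting ends (Versions 2 and 3; low importance)

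*Combined protocol and SAP*

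**What the plan says.** The text is the same in Versions 2 and 3 on each of these points.

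- **Promised follow-up.** Synopsis, Description of Study: "All patients will be followed for 60 days from the time of study drug administration". Synopsis, Length of Study: "A follow-up period beginning at hospital discharge through 60 days post study drug".
- **Endpoints at the last study day.** The synopsis and Section 3.3.3 list "All-cause readmission at Day 30 and Day 60", and all-cause mortality at Days 14, 30 and 60. Section 6.4.2 analyses mortality as a hazard ratio and readmission as a proportion.
- **Final visit.** Section 3.1.1 and Appendix 1b place it at Day 60 ± 4 for discharged patients. The Appendix 1b column is headed "Day 60 ± 4 (Study Completion) or Early Discontinuation" and is the last one in that schedule. Section 4.9.3: "Patients who complete all study visits through Day 60 are considered to have completed study".
- **Missing data.** Section 6.4 censors patients lost to follow-up when they were last known to be event-free. It allows no imputation beyond that censoring.
- **End of adverse-event reporting.** Section 5.3.1: events "will be reported until the Day 60 visit or Early Discontinuation visit". Section 5.2.1 monitors events through Day 60, and Section 5.4.2.2 has serious events and events of special interest reported until Day 60; neither refers to the visit. Section 5.5 refers to "the end of the adverse event reporting period (defined as 60 days after the dose of study drug".

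**The concern.** A symmetric window does little harm at Day 14 or Day 30, because a later visit can recover a patient's status on the nominal day. At the last visit nothing follows. A discharged patient seen on Day 56 has completed the study, yet readmission on Days 57–60 belongs to the endpoint and no scheduled contact would detect it. Section 6.4 does not say whether such a patient counts as not readmitted, on incomplete follow-up, or as missing. At stake are a slight undercount in one secondary proportion and an analysis choice left open until the data are in hand.

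The reporting period is a second, separate inconsistency. Read literally, Section 5.3.1 can close reporting up to four days before the other sections do, so sites have no single end date to work to.

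**Working it through.** **The plan's own figures.** The plan states no share of visits before Day 60, so there is none to reproduce. Its design figures do reproduce:

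- Enrolment: 300/(1 − 0.10) = 333.3, rounded up to 334.
- Power, with about 300 events and power = Φ(½·√d·|ln HR| − z): HR 0.80 at two-sided alpha 0.2 gives Φ(1.93 − 1.28) = 74.2%, against 75% stated.
- At alpha 0.05, HR 0.60, 0.70 and 0.80 give 99.3%, 87.1% and 48.9%, against 99%, 86% and 48% in Table 7.

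These figures concern the primary endpoint (assumed control median 5 days) and do not depend on the Day 60 window.

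**Share of visits before Day 60.** The window runs from Day 60 − 4 = 56 to Day 60 + 4 = 64, nine days, of which four precede Day 60. The distribution of visits is my assumption:

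- Even spread: 4/9 = 44.4%.
- Triangular, centred on Day 60: 40%.
- Normal, centred on Day 60, SD 1, 1.5, 2 or 3 days: 30%, 37%, 40% or 42%.
- Limits set by the window alone: 0% to 100%.

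**Number of patients.** Only survivors discharged before Day 60 have this visit. Section 3.2.2 gives a mortality of 9–32% for this population. Taking that as the Day 60 risk:

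- 300 × (1 − 0.09) = 273, and 273 × 4/9 ≈ 121.
- 300 × (1 − 0.32) = 204, and 204 × 4/9 ≈ 91.

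So about 91–121 patients under even spread, and fewer with undetermined status, because anyone readmitted before the visit is already known to be a case.

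**Time unobserved.** At most 4 of 60 days (6.7%) per patient. Under even spread the mean is (4 + 3 + 2 + 1)/9 = 1.1 days.

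**Readmissions missed.** The documents give no readmission risk. I assume p = 10–25% over Days 7–60 (53 days) at constant hazard h = −ln(1 − p)/53. The chance that a first readmission falls in the last k days is (1 − p)(e^(kh) − 1). Per 300 patients:

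- p = 10%: h = 0.00199. All visits on Day 56: 300 × 0.90 × (e^(4h) − 1) = 2.2. Even spread, summing over k = 1 to 4 and dividing by 9: 0.6.
- p = 25%: h = 0.00543. All visits on Day 56: 300 × 0.75 × (e^(4h) − 1) = 4.9. Even spread: 1.4.

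This treats all 300 as discharged survivors, so it errs high. Readmissions clustered early would reduce it further.

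**Deaths, for comparison.** With 9–32% as Day 60 risk and constant hazard over 60 days, 0.5–1.5 deaths per 300 fall after the last visit under even spread, and 1.7–5.3 if all visits are on Day 56. Censoring at last contact takes the patient out of the risk set for those days instead of counting the patient as a Day 60 survivor.

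**The case against.** The strongest case against is that this is immaterial. By the arithmetic above about one readmission in 300 is lost, in one of about a dozen secondary endpoints, in a study that Section 6 says will do no formal hypothesis testing. That stands, and it is why the point ranks low.

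Four stronger readings are tempting and are not supported:

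- **Nearly half of completers lack Day 60 status.** A reader might infer this from 4/9. That figure needs evenly spread visits, which the documents do not state. It applies to discharged survivors only, and those readmitted before the visit have known status.
- **Day 60 mortality is compromised in the same way.** It is analysed as a hazard ratio with censoring, which handles a Day 56 visit with little loss.
- **Deaths and serious events on Days 57–60 reach the sponsor only by chance.** Sections 5.2.1 and 5.4.2.2 already run to Day 60, and Section 5.5 to 60 days after the dose. Only Section 5.3.1 ties the end to the visit. What remains true is that no contact is scheduled after the visit to find such events.
- **The repair is free.** With about 170 centres planned, a narrower window could produce more out-of-window visits.

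Two limits also stand. The file shows a later Version 5 (Global) whose body was not available, so whether the window persists there is unchecked. Section 6 defers further analysis detail to a separate SAP; a counting rule may be there.

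**Conclusion.** In Versions 2 and 3 the final-visit window does not match the promised 60 days of follow-up or the Day 60 readmission proportion, and no rule covers patients last seen on Days 56–59. This follows from the text without any assumption. Its size does rest on assumptions: the visit distribution and the readmission risk. Within the ranges shown, the loss is between under one and about five readmissions per 300. It should be similar in both arms, since both share the same window under blinding. The disagreement between Section 5.3.1 and Sections 5.2.1, 5.4.2.2 and 5.5 also needs no assumption. Neither affects the primary endpoint or power. This is a cheap improvement, not a threat to the trial's conclusions.

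**What to change.** - In Section 3.1.1 and Appendix 1b, open the final window at Day 60: for example Day 60 to Day 64, or Day 60 to Day 68 to keep the present nine-day width. The share of in-window final visits before Day 60 then becomes zero.
- At that visit, ascertain vital status and readmission through Day 60, and count only events with onset up to Day 60 in the Day 60 endpoints.
- State in Section 6.4 or the SAP how a patient last seen before Day 60 counts in the readmission proportion.
- Reconcile Section 5.3.1 with Sections 5.2.1, 5.4.2.2 and 5.5 so that reporting does not end before Day 60. Say how days are numbered: the infusion is on Day 1, so 60 days after the dose could mean Day 61.
- Check first whether Version 5 retains the window.

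**Cost.** Wording only, with no added visit or assessment. Ending at Day 64 leaves five scheduling days instead of nine; ending at Day 68 makes final visits and the laboratory, ECG and pharmacokinetic samples slightly later on average. If neither suits, a brief Day 60 contact for vital status and readmission closes the same gap, at the price of one added contact.
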